10. SECONDARY ANALYSES

Secondary analyses will evaluate the effect of A-tDCS vs sham on change in lexical features of discourse, Content Units (CU) and syllables/CU in describing the Cookie Theft picture, HANA, NIH Stroke Scale, SIS, mRS, and PHQ-9.

For continuous measures, the secondary analyses will be adjusted for aphasia type (Anomia, Broca, or other type), baseline aphasia severity (AQ), and age using a linear mixed effects regression to compare treatment groups. The model will include repeated measures of change from baseline to 1, 5, 20 weeks post and visit will be a classification variable with interaction terms for visit*treatment group (SAS PROC MIXED with a REPEATED subcommand).

```
PROC MIXED;
  CLASS SUBJID ARM VISITNUM TYPE;
  MODEL CHANGE= ARM|VISITNUM WABAQ TYPE AGE;
    REPEATED VISITNUM / TYPE= CS SUBJECT=SUBJID R RCORR;
  LSMEANS ARM*VISITNUM/pdiff CL;
RUN;
```

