6. Administer the NIH Stroke Scale (NIHSS) (Lyden et al, 1999): Clinicians will be certified in administration of the NIHSS by taking a web-based course offered by the American Heart Association. The NIHSS will provide a measure of overall stroke severity. The SLP will also record the description of the "Cookie Theft" picture on the NIHSS, which will also be analyzed for Content Units (CU) and Syllable/CU (Craig et al., 1993; Yorkston & Beukelman, 1980). This test will be repeated at Week 5 and Week 20 after the end of treatment.

7. Administer the Stroke Impact Scale (SIS) (Duncan et al., 1999).

Procedures for the Computerized Naming Assessments (Visits 1, 2 & all follow up evaluations)

The following procedures will be performed during Visits 1, 2, and each follow-up evaluation:

1. Turn on the laptop computer and position in front of the participant.
2. Set up and start internal web-camera for audio-visual recording. Administer the PNT on a laptop computer. Instruct the participant to overtly name each picture as soon as it is displayed. Trials will end following a response or after 10-seconds have elapsed, in which the administrator will say the correct picture name in order to discourage perseveration on subsequent trials.
3. Stop web-camera and save video file for later scoring of naming.
4. Start internal web-camera for audio-visual recording. Administer the Naming 80 Assessment (naming of 80 items from the training set) on a laptop computer. Instruct the participant to overtly name each picture as soon as it is displayed. Trials will end following a response or after 10-seconds have elapsed.

Procedures for the "Cinderella Story" Picture Discourse Analysis and Depression Scale (Visit 2, 18, 20, and corresponding baseline and follow-up evaluations for each treatment period)

The following procedures will be performed during Visits 2 (baseline), 18 (immediately after), 20 (5 week follow-up), and corresponding baseline and follow-up times for each treatment period, as well as 6 months after both the acute phase and the subacute phase.

1. The "Cinderella Story" is to be completed following the administration of the naming assessments, so the laptop computer and web-camera set-up will need to remain for this portion of the assessment.
2. Place the picture book in front of the participant.

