6. RANDOMIZATION AND BLINDING

The study is to be conducted in a double-blind manner. The subjects, the site investigators, and the clinical staff involved in this study will not know the intervention assignment. Select members of the Data Coordination Unit (DCU) will be partially blinded, i.e., they will know the intervention group assignment as A or B, but not whether the patient receives active tDCS (A-tDCS) or sham (S-tDCS).

The randomization will take place centrally via the Trial Website (WebDCU). Subjects will be randomized 1:1 (A-tDCS: S-tDCS). The objective of subject randomization is to protect the randomness of treatment allocation and to prevent serious imbalances in baseline age, aphasia type, and severity (as measured by the Western Aphasia Battery revised WAB-R). The block urn method (Zhao et al. 2011) and the minimal sufficient balancing method (Zhao et al. 2012) will be used. The computer program developed at the DCU makes the treatment assignment based on the current status of treatment group distribution within each stratum as well as overall balance of treatment assignment.

A “Real-Time” randomization procedure is implemented via the Trial Website on the WebDCU™ System where the clinical center staff enters the baseline (e.g., age, aphasia type, and AQ severity) and eligibility information of a subject prior to enrollment. If the subject’s eligibility status is confirmed, the computer program on the WebDCU™ server will evaluate the treatment arm distribution and generate a treatment assignment based on the randomization scheme.

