7. BASELINE INTERVENTION GROUP COMPARABILITY

Summary statistics for the following baseline variables will be compared between treatment groups. At study conclusion the statistical tests for comparison will be two-sample *t*-test or Wilcoxon rank sum test for continuous scale variables and chi-square or exact test for categorical variables.

Baseline Characteristics, Mean (SD); Median (IQR)	Active-tDCS (N=)	Sham-tDCS (N=)	p-value
Age			
Male sex, frequency (%)			
Race, frequency (%)			
White			
Black			
Other			
Hispanic, frequency (%)			
Years of Education			
Stroke Onset to Enrollment (days)			
Aphasia Type, frequency (%)			
WAB-R AQ			
Current use (at randomization), freq (%)			
SSRIs Antidepressants			
Mixed /Atypical SSRIs			
Non- SSRIs Antidepressants			
Anxiolytics/Antipsychotics			
Anticholinergic Agents			
Dementia medications			
Past medical history, frequency (%)			
Chronic Pain			
Average # headaches/month			
Seizures			
Surgery			
Allergies			
Depression			
Diabetes			
Exercise 20 minutes (times/week)			
Exercise prior to stroke (times/week)			
mRS			
NIHSS			
BNT			
ASRS			
PPTT			
PNT correct			
Naming 80			
PHQ-9			
SIS-16			
Hopkins Action Naming Assessment (HANA)			
Content Units (CU)			
Syllable/CU			
Current Occupation			
.....			
.....			

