8.5 Missing Data

For the primary analysis, for participants who do not complete the 1 week post-treatment assessments, the post-treatment value will be imputed using a multiple imputation approach assuming a FCS missing mechanism and missing is at random (MAR).

As a sensitivity analysis with the modified ITT sample, the primary outcome analysis will be repeated using all available follow-up data (without explicit imputation) in a mixed effects model of the change from baseline in naming accuracy adjusted for baseline (with week (1, 5, or 20 weeks post-treatment) as class variable and a REPEATED statement). The model will include the baseline covariates used for the primary analysis as fixed effects.

The statistical model will be a repeated measures model (SAS® MIXED procedure with REPEATED subcommand) assuming a compound symmetry (CS) covariance structure.

```
PROC MIXED;
  CLASS SUBJID ARM VISITNUM TYPE;
  MODEL CHANGE= ARM|VISITNUM WABAQ TYPE AGE;
    REPEATED VISITNUM / TYPE= CS SUBJECT=SUBJID R RCORR;
  LSMEANS ARM*VISITNUM/pdiff CL;
RUN;
```

The least square (adjusted) mean for each treatment group, and the 95% confidence interval for the comparison (active vs. sham) will be presented at 1, 5, 20 weeks post treatment.

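### SAP 10 models continuous secondary outcomes as change without adjusting for their own baseline: valid under randomisation, but less precise than it could be and sensitive to chance baseline imbalance

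*SAP*

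**What the plan says.** SAP 10 lists the secondary outcomes as lexical discourse features, Content Units, syllables/CU, "HANA, NIH Stroke Scale, SIS, mRS, and PHQ-9". For the continuous ones, "the secondary analyses will be adjusted for aphasia type (Anomia, Broca, or other type), baseline aphasia severity (AQ), and age". The response is change: "The model will include repeated measures of change from baseline to 1, 5, 20 weeks post". The code agrees with the text: "MODEL CHANGE= ARM|VISITNUM WABAQ TYPE AGE". Baseline is therefore neither a covariate nor a response row.

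The baselines exist. SAP 7 says "Summary statistics for the following baseline variables will be compared between treatment groups", and its table has rows for mRS, NIHSS, PHQ-9, SIS-16, HANA, CU and Syllable/CU. The protocol's procedure for the Cinderella discourse task and the PHQ-9 gives its timing as "The following procedures will be performed during Visits 2 (baseline), 18 (immediately after), 20 (5 week follow-up".

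SAP 6 gives the balancing aim of the randomisation as "to prevent serious imbalances in baseline age, aphasia type, and severity". These are the three covariates already in the model. No secondary baseline is among them.

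Own-baseline adjustment appears elsewhere only for naming. SAP 8.5 describes its sensitivity model as "change from baseline in naming accuracy adjusted for baseline", yet its MODEL line is the same as in SAP 10 and has no baseline term. Hypothesis 2b in SAP 11 adjusts for baseline naming accuracy. The protocol's longitudinal model (Post-Testing Phase), which it says may be extended to other secondary outcomes, has no own-baseline term either.

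**The concern.** A change score subtracts the whole of any baseline difference between the arms, although only part of that difference is expected to persist to follow-up. Two things follow, and they are two views of the same variance. The contrast has a larger standard error than a baseline-adjusted contrast. And in a given trial, the arm that happens to start worse will tend to show the larger gain.

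With 40 to 50 participants, precision is scarce. AQ is a language score and cannot be expected to stand in for baseline mood, stroke impact or neurological severity. SAP 7 will test the arms for baseline differences but names no remedy if, say, PHQ-9 differs. That leaves room for adjustment decided after the data are seen.

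**Working it through.** **The plan's own figure.** The only power statement (SAP 8.3) concerns the primary outcome: 20 per group, difference 23, SD of change 22.2, two-sided alpha 0.05, power 89%. The noncentral t gives 0.891 and the normal approximation 0.906, so the figure is reproduced and is not in dispute. No power is stated for any secondary outcome. I use 20 per arm from SAP 8.3 and 25 per arm from the goal in SAP 4 (50 participants with a week-1 PNT, 1:1).

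**Assumptions.** rho is not in the documents; 0.4 to 0.9 is assumed. Baseline and follow-up have equal SD, set to 1, and one follow-up visit is considered.

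**Formulas.**
- Variance factor, change score: 2(1 - rho). With own baseline: 1 - rho². Ratio: (1 + rho)/2.
- Equivalent extra participants: 2/(1 + rho) - 1.
- Shift of the change contrast for a baseline difference d: (1 - rho) × d in size, in the opposite direction to d on the outcome scale.
- SE of the change contrast with n per arm: sqrt(2(1 - rho) × 2/n).

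| rho | variance ratio | extra participants | shift at d = 0.3 SD | shift / SE, n = 20 | shift / SE, n = 25 |
|---|---|---|---|---|---|
| 0.4 | 0.70 | 43% | 0.18 SD | 0.52 | 0.58 |
| 0.5 | 0.75 | 33% | 0.15 SD | 0.47 | 0.53 |
| 0.7 | 0.85 | 18% | 0.09 SD | 0.37 | 0.41 |
| 0.8 | 0.90 | 11% | 0.06 SD | 0.30 | 0.34 |
| 0.9 | 0.95 | 5% | 0.03 SD | 0.21 | 0.24 |

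**How likely is a 0.3 SD difference?** The SE of the baseline difference is sqrt(2/20) = 0.316 SD or sqrt(2/25) = 0.283 SD. The two-sided probability of at least 0.3 SD is 2[1 - Phi(0.949)] = 34% or 2[1 - Phi(1.061)] = 29%.

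**Does AQ already do the job?** Suppose AQ correlates equally (r) with the baseline and the follow-up of an outcome. Then its covariance with change is r - r = 0, and adjusting for it leaves the change-score variance at 2(1 - rho). With AQ in both models and r from 0.3 to 0.5, the variance ratio is 0.73 to 0.67 at rho 0.5 and 0.84 to 0.80 at rho 0.7. So the gain from own baseline is slightly larger than without AQ.

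A simulation under the null (25 per arm, 6,000 trials per setting, AQ in both models) gave:

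| rho, r | mean estimate, change / with baseline | SD, change / with baseline | slope on baseline imbalance, change / with baseline |
|---|---|---|---|
| 0.5, 0.3 | 0.001 / -0.003 | 0.286 / 0.246 | -0.50 / -0.01 |
| 0.7, 0.3 | -0.002 / -0.001 | 0.219 / 0.205 | -0.28 / 0.02 |
| 0.7, 0.5 | 0.005 / 0.005 | 0.220 / 0.199 | -0.30 / -0.00 |

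Both estimators average about zero. Only the change score follows the baseline imbalance.

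**The case against.** A reader might infer that the planned comparison is biased by regression to the mean, or that its type I error is inflated. The documents do not support that. Allocation is randomised 1:1, so across randomisations the change contrast is unbiased, as the simulated means confirm. The shift exists only conditional on an imbalance that arose by chance.

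A reader might also infer that every secondary comparison is affected to the same degree. That does not hold either:
- SAP 10 gives this model for continuous measures only and does not say how the ordinal mRS is handled.
- HANA, CU, syllables/CU and the discourse features are language measures, so balancing on WAB-R severity makes a large baseline imbalance in them less likely. If AQ were perfectly balanced and correlated 0.5 to 0.7 with such a baseline (assumed), the 29% at 25 per arm would fall to about 22% to 14%. The imbalance that remained would still shift the contrast.

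The size is also uncertain. At rho 0.8 to 0.9 the gain is worth only 11% to 5% more participants, and the lost degrees of freedom eat into it.

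Finally, the stakes are limited. SAP 8.4 treats these outcomes as supportive, without alpha adjustment, and the protocol ties the Phase III decision to the primary hypothesis. All of this stands. It limits the weight of the point, but it is no reason to leave collected baselines out of the model.

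**Conclusion.** The omission is a matter of fact: text and code in SAP 10 agree, and no other section supplies own-baseline adjustment for the secondary outcomes. The planned analysis is valid. It gives up precision and leaves the estimate exposed to chance imbalance, most plainly for NIHSS, SIS and PHQ-9, for which neither the balancing nor the AQ covariate is a substitute.

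Over the assumed rho of 0.4 to 0.9, the standard error is 16% down to 3% larger than needed when measured as the reduction available (1 - sqrt(0.70) = 0.16; 1 - sqrt(0.95) = 0.03). These sizes rest on the assumed rho, equal SDs and a single visit; the direction of the argument does not depend on where rho falls in that range. This is a worthwhile improvement to supportive analyses and casts no doubt on the primary result.

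**What to change.** In SAP 10, for each continuous secondary outcome, use `MODEL CHANGE = ARM|VISITNUM BASE BASE*VISITNUM WABAQ TYPE AGE;`, where BASE is that outcome's own baseline, kept continuous (not in the CLASS statement). Say so in the text, and state which outcomes count as continuous and how mRS is analysed.

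In SAP 8.5, add the same two terms with baseline PNT as BASE, so that the code does what its text promises. The primary regression in SAP 8.2 also lists no baseline PNT. That is a separate decision, but it is sensible to settle it at the same time.

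The cost is a sentence and one line of code per model, and up to three degrees of freedom (one for BASE, two for its interaction with three visits). No new data are needed. SAP 2 foresees an update before database lock and unblinding, which is the time to make the change.

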11. EXPLORATORY SUBGROUP ANALYSES

Exploratory analyses will also examine if any effects of A-tDCS vary across participants with different characteristics such as SSRI use, age (<55 vs. ≥55), education (<11 years completed vs. ≥12 years), time since stroke onset to initiation of treatment (<1 month vs. ≥1 month), and lesion volume. To address this, a regression of change in naming accuracy, which includes main effects and interaction terms with treatment group for these characteristics, will be used. Given the small sample size and since this is a secondary analysis, a significance level of 0.10 will be used to retain main effects or interaction with treatment in the final reported model. Finally, within the tDCS treatment group, we will compare mean change in naming untrained pictures for the fMRI versus the structural placement (CRF501 Q01) subgroups.

```

PROC MIXED;
  CLASS SUBJID ARM TYPE SUBGROUP;
  MODEL CHANGE=ARM | SUBGROUP WABAQ TYPE AGE;

  LSMEANS ARM*SUBGROUP/pdiff CL ALPHA=0.1;
RUN;

```

Hypothesis 2a: To test the hypothesis that within the first 3 months after stroke, improvement in naming untrained pictures is negatively influenced by increased time to initiate treatment; but this effect of time is mitigated by taking SSRIs continuously from stroke onset, we will carry out the secondary analysis as initially described above by comparing model 1 with model 2 as follows:

- Model 1 will be a linear regression of change in naming accuracy from baseline to 1 week post-treatment with the following regressor/predictor variables: treatment group (A-tDCS or sham), WABAQ, age, education, time from stroke onset to initiation of treatment (in days).
- Model 2 will include the regressors from models 1 and an indicator of SSRI use since baseline (yes= if patient had used SSRIs continuously from stroke onset, no=otherwise). We predict that in model 1, time from stroke onset to initiation of treatment (in days) will be negatively associated with the response variable. In model 2, we predict that time from stroke onset will no longer be associated with outcome; after adjusting for SSRI use (and all else in the model), the type III test for the effect of time from stroke onset will not be statistically significant and the magnitude of the parameter estimate will change by more than 10%.

Hypothesis 2b: To address the hypothesis that SSRI use since stroke onset is associated with greater gains with all treatments in the subacute period, independently of depression, we will collapse participants across treatment groups, and compare the primary outcome measures for participants who have continuously taken SSRIs to participants who have not taken SSRIs. If SSRI use enhances plasticity at the subacute stage, it might augment the effect of A-tDCS and naming therapy without tDCS. Participants who have taken SSRIs for only part of the time will not be included in the analysis. The adjusted mean change (95% CI) in naming accuracy on untrained stimuli from baseline to 1 week, 5 weeks, and 20 weeks post-treatment for the SSRI-treated and the SSRI-untreated groups will be estimated using a mixed effects model adjusting for treatment group, baseline naming accuracy, time (with week 1, 5, or 20 as a categorical variable and a random effect for subject), and any baseline subject characteristic found to be statistically significant in the primary or subgroup analyses. We will then evaluate the independent effects of SSRI use, depression (measured at each time point with PHQ-9 score of ≥ 15), and tDCS vs sham on the primary outcome graphically. Although we may not have the power to detect a significant effect of SSRIs, a few studies with similar small numbers have reported significant effects of SSRIs on stroke recovery measured with less sensitive measures such as the mRS. The goal of this exploratory aim is to determine whether or not we need to control for SSRI use in a subsequent clinical trial of A-tDCS in subacute stroke.

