Secondary Analyses: In secondary analyses, we will evaluate the effect of A-tDCS versus sham on change in lexical features of discourse, NIH Stroke Scale (NIHSS) (Lyden et al., 1999), modified Rankin Scale (mRS) (Banks et al., 2007; Rankin 1957), Stroke Impact Scale (Duncan et al., 1999) as well as Content Units (CU) and syllable/CU in the "Cookie Theft" picture description (Craig et al., 1993; Yorkston & Beukelman, 1980). Secondary analyses will also examine if any effects of A-tDCS vary across participants with different characteristics such as SSRI use, age, education, time of initiation of treatment, previous SALT, and lesion volume. To address this, a regression of change in naming accuracy, which includes main effects and interaction terms with treatment group for these characteristics will be used. This model will be adjusted for treatment and time as described above for the mixed effects model. Given the small sample size and since this is a secondary analysis, a significance level of 0.10 will be used to retain main effects or interaction terms with treatment in the final reported model. Finally, within the tDCS treatment group, we will compare mean change in naming untrained pictures for the fMRI localization versus the structural localization subgroups (n=10-13 per subgroup). If there is a trend for the fMRI localization subgroup to show greater gains than the structural localization subgroup, we will include this comparison in a Phase III trial.

Secondary Objectives

Date: March 2, 2021

Principal Investigator: [name], MA

Application Number: IRB00089018

Hypothesis 1b: The effect of A-tDCS will be greater in subacute stroke than reported in chronic stroke, the mean (95% CI) changes from baseline to 1 week, 5 weeks, and 20 weeks after the end of treatment will be reported for the subacute patients enrolled in this project and the chronic stroke patients enrolled in the Transcranial Direct Current Stimulation to Treat Aphasia: Phase II Trial (U01 DC011739; CATES Trial; PI: [name]) conducted at the University of South Carolina and the Medical University of South Carolina. The current trial is being conducted in collaboration with our colleagues at Medical University of South Carolina and University of South Carolina, including [name], who has designed and published previous studies using the computer-delivered SALT.

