8.4 Multiplicity

The primary analysis and sensitivity analyses will be tested at two-sided alpha of 0.05. For secondary outcomes, no adjustment of Type I error probability will be considered, since they will be considered supportive of the primary analysis. Tests for interaction with baseline covariates and treatment will use two-sided alpha of 0.10, since they will be treated as exploratory.

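### SAP section 11 tests treatment interactions on two-group versions of age, education and time since stroke; if modification is roughly linear, continuous terms would keep information that these splits lose

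*SAP*

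**What the plan says.** SAP section 11 (Exploratory Subgroup Analyses) describes a regression of change in naming accuracy "which includes main effects and interaction terms with treatment group for these characteristics, will be used". Age is split at 55. The other two splits read "education (<11 years completed vs. ≥12 years" and "time since stroke onset to initiation of treatment (<1 month vs. ≥1 month". Lesion volume is listed without a cut. The code has "CLASS SUBJID ARM TYPE SUBGROUP" and "MODEL CHANGE=ARM | SUBGROUP WABAQ TYPE AGE", so the modifier is categorical while age also stays in the model as a continuous covariate.

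SAP section 8.4 sets the error rate: "Tests for interaction with baseline covariates and treatment will use two-sided alpha of 0.10". Section 11 uses the same 0.10 level to decide which terms remain in the final reported model. Hypothesis 2b then adjusts for baseline characteristics that reach significance in the primary or subgroup analyses.

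The protocol's version of this analysis (section 2, Secondary Analyses) names "age, education, time of initiation of treatment, previous SALT, and lesion volume" with no cut-points. SAP section 2 says the final SAP overrides the protocol, so the split version governs. Under Hypothesis 2a the SAP keeps "time from stroke onset to initiation of treatment (in days" as a regressor. The baseline table in SAP section 7 lists age, years of education and days from stroke onset to enrolment, so continuous values are collected.

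**The concern.** A treatment-by-covariate test in 40 to 50 people is weak to begin with. Replacing a measured continuous modifier by a two-level one weakens it further when the modification is gradual, and ties the answer to where the cut falls. Section 11 gives no reason for any of the three cuts.

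Hypothesis 2a does not fill the gap. Its two models contain days from onset as a main effect only, so the split is the SAP's only test of whether time since stroke modifies the treatment effect.

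There are two specification gaps as well. A participant with exactly 11 years of education has no `SUBGROUP` value and would drop out of that model. Lesion volume has no stated cut, yet the code's `SUBGROUP` is a class variable, so either a cut must be chosen later or the code must change.

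What is at stake is the final reported model and the Hypothesis 2b covariate set.

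**Working it through.** **Inputs from the documents.** SD of change 22.2, difference 23, 20 per group, two-sided alpha 0.05 (SAP 8.3). Interaction alpha 0.10, two-sided (SAP 8.4). Allocation 1:1, and a target of 50 with a 1-week PNT (SAP 4). Expected completers 40-45 (Protocol 2, Power). Stroke within 90 days (SAP 5.1).

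**Assumptions.** The shapes of the modifier distributions, a linear modification, and one month taken as 30 days.

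**Step 1: the plan's own figure.** The documents give no power figure for the interactions. The nearest is the primary 89%. The noncentrality is 23 / (22.2 × √(2/20)) = 23 / 7.02 = 3.28. With 38 degrees of freedom and two-sided alpha 0.05, power is 89.1%, so the figure reproduces.

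**Step 2: information kept by a split.** For a linear modifier this is the squared correlation between the variable and its split. With share p below the cut:
- normal: φ(z_p)² / [p(1−p)]
- uniform: 3p(1−p)

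For example, the normal median split gives 0.399² / 0.25 = 0.637. The normal 20/80 split gives 0.280² / 0.16 = 0.490. Uniform 0-90 days cut at 30 gives 3 × 1/3 × 2/3 = 0.667.

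| Assumed distribution | Share below cut | Kept | Lost | 40 worth | 50 worth |
|---|---|---|---|---|---|
| Uniform | 1/2 | 0.750 | 25% | 30.0 | 37.5 |
| Uniform (time, cut at 30 of 90 days) | 1/3 | 0.667 | 33% | 26.7 | 33.3 |
| Normal | 1/2 | 0.637 | 36% | 25.5 | 31.8 |
| Normal | 1/5 | 0.490 | 51% | 19.6 | 24.5 |
| Normal | 1/10 | 0.342 | 66% | 13.7 | 17.1 |

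For age, an assumed mean of 60-65 and SD of 11-13 puts 18-35% below 55, and the loss is 40-53%.

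**Step 3: simulated power.** The arm-by-modifier test was simulated at alpha 0.10 with SD 22.2 and 4,000 runs per setting. The treatment effect was made to change by 17.5 items per SD of the modifier at N=40, and by 15.6 at N=50.
- Continuous term: 73-78%.
- Normal median split, or uniform one-third split: 58-61%.
- Normal 20/80 split: 46-47%.
- Uniform median split: about 66%.

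Type I error, checked for the uniform one-third split, was about 0.10 for both the continuous and the split test. The cost of splitting is therefore power, with no gain in error control.

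**Step 4: scale of the two-group test.** At N=40 the SE of the main effect is 2 × 22.2 / √40 = 7.02. The SE of a two-group interaction is 7.02 / √[p(1−p)], which is 14.0 at 50/50 and 17.6 at 20/80. An interaction of 23, the whole planned effect, has power Φ(23/14.04 − 1.645) = 50% and Φ(23/17.55 − 1.645) = 37%. At N=50 the figures are 57% and 43%. Much of this weakness comes from the sample size, and the split adds to it.

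**The case against.** The strongest objection is that the gain depends on linearity. If the true modification is a step at 30 days and time is uniform, the same squared correlation applies in reverse: a linear term in days keeps 66.7% and the split keeps everything. The protocol's background section (tDCS in Aphasia Research) offers partial support for a one-month threshold, since it describes a sensitive period of roughly the first month after stroke. That passage concerns motor training, however. It goes on to say that the period for language may last up to three months, which is the whole eligibility window, and SAP section 11 does not cite it. The point stands for time to the extent that a one-month split deserves a supporting role. No comparable rationale was found for the age or education cuts.

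A reader might infer that the SAP contradicts itself or the protocol. It does not. Hypothesis 2a asks a different question of days from onset, continuous age as an adjustment covariate can sit beside an age-group interaction, and the protocol left the functional form open for the SAP to settle. The stated cuts are also fixed in advance, so they are not data-driven.

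The tests are labelled exploratory and the SAP acknowledges the small sample. Both facts are right and limit the importance of the point.

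**Conclusion.** The point holds as an efficiency and specification matter in exploratory analyses. Under a roughly linear modification the splits lose about 33% (uniform time cut at 30 days) to 36-51% (normal, 50/50 to 20/80), with about 25-66% as the wider plausible range.

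It would be tempting to state a loss of a third to a half as a property of this trial. The documents do not support that. They give no distribution for age, education or time beyond the 90-day limit, and there is no such loss if the effect is a step at the cut.

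Nor should a reader infer a threat to the main result. The SAP's primary model lists AQ and age without cuts, and the protocol's decision about a Phase III study rests on the primary test. The practical consequence is confined to which terms are retained at 0.10 in the final reported model and which covariates enter Hypothesis 2b. The 11-year education gap and the uncut lesion volume are plain drafting gaps that need no distributional assumption.

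**What to change.** Make the interaction tests `ARM` by continuous age, `ARM` by years of education and `ARM` by days from onset to treatment. Enter lesion volume as a continuous term and not in `CLASS`. When age is the modifier, the existing `AGE` term serves as its main effect. SSRI use can stay categorical.

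Plot change against each modifier by arm to check linearity. Keep the two-group estimates as a display, with the education groups redefined so that 11 years belongs to one of them. The one-month split may be kept as a supporting analysis, with the sensitive-period background cited as its reason.

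The cost is a few model terms and plots. No new data are needed, and SAP section 2 already foresees an update before database lock. The downside is the assumption of linear modification, which the plots can check only roughly at this sample size. The tests will remain weak after the change and should still be reported as exploratory.

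### Dropping subgroup terms that miss p<0.10 inflates the interactions that remain, and the SAP's own code does not do it; Hypothesis 2b covariates should also be fixed in advance

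*SAP*

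**What the plan says.** SAP section 11 asks "if any effects of A-tDCS vary across participants with different characteristics such as SSRI use, age", and then names education, time since stroke onset and lesion volume. That makes five characteristics, in a list left open by its wording. It calls for a regression "which includes main effects and interaction terms with treatment group for these characteristics, will be used", and adds that "a significance level of 0.10 will be used to retain main effects or interaction with treatment in the final reported model". The protocol, under Secondary Analyses in section 2, has the same rule: "a significance level of 0.10 will be used to retain main effects or interaction terms with treatment in the final reported model".

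The code printed in SAP section 11 differs. Its model statement is "MODEL CHANGE=ARM | SUBGROUP WABAQ TYPE AGE", which reads as one subgroup factor at a time with fixed covariates. Its output statement is "LSMEANS ARM*SUBGROUP/pdiff CL ALPHA=0.1", which gives 90% limits. Nothing in it drops a term.

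On status, SAP 8.4 says "Tests for interaction with baseline covariates and treatment will use two-sided alpha of 0.10, since they will be treated as exploratory".

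For Hypothesis 2b, also in SAP section 11, the SSRI comparison always adjusts for treatment group, baseline naming accuracy and time, with a random subject effect. It then adds "any baseline subject characteristic found to be statistically significant in the primary or subgroup analyses". That sentence gives no significance level. SAP 8.4 uses 0.05 for the primary and sensitivity analyses and 0.10 for interactions. The protocol's version adds whichever listed characteristics prove important in the secondary analysis.

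**The concern.** The difficulty is the filter, not the 0.10 level. In 40 to 50 people an interaction is estimated with a large standard error, so only large estimates pass. The terms left in the reported model are therefore selected for being large, and an ordinary interval takes no account of that. Neither document describes shrinkage, resampling or another post-selection correction, and neither says that dropped terms will also be shown. A reader of the final model could take a chance finding, or a modest effect modifier, for one as large as the treatment effect itself.

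The sentence and the code also describe different procedures, so an analyst cannot follow both.

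Hypothesis 2b raises a separate issue. SSRI use is not randomised. Whether a covariate reaches significance for the outcome in a small trial does not show whether it confounds the SSRI comparison, and a real confounder can easily be missed. The stated purpose of this aim is to decide whether a later trial must control for SSRI use.

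**Working it through.** **Inputs from the documents.** SD of change 22.2, planned difference 23, 20 per group, two-sided alpha 0.05, power 89% (SAP 8.3). Target of 50 with the 1-week PNT (SAP section 4); 40–45 completers expected (protocol, Sample Size Determination). Retention level 0.10 and five named characteristics (SAP section 11).

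**Assumptions not in the documents.** Two-level subgroups split evenly and balanced across arms; true interactions of 0, 10 or 23 items; residual SD equal to the unadjusted 22.2, although the model adjusts for AQ, aphasia type and age.

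**The plan's own figure.** A noncentral t calculation with 38 df, difference 23 and SE 22.2 × √(2/20) = 7.02 gives power 0.891. The stated 89% reproduces.

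**Retention threshold.** With N/4 people per cell, the interaction (a difference of two treatment differences) has SE = 22.2 × √(4/(N/4)).
- N=40: 22.2 × √(4/10) = 14.04. With t(0.95, 36 df) = 1.688, the threshold is about 23.7 items.
- N=50: 22.2 × √(4/12.5) = 12.56. With t(0.95, 46 df) = 1.679, the threshold is about 21.1 items.

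**What survives the filter.** Simulation of one interaction, kept if p<0.10:

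| True interaction | N | Probability kept | Mean absolute kept estimate | 90% CI coverage if kept |
|---|---|---|---|---|
| 0 | 40 | 10% | 28.4 | 0% |
| 0 | 50 | 10% | 25.5 | 0% |
| 10 | 40 | 18% | 30.2 | 67% |
| 10 | 50 | 20% | 27.4 | 72% |
| 23 | 40 | 49% | 34.3 | 90% |
| 23 | 50 | 56% | 31.6 | 91% |

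For a true value of 0 the signed mean is zero; the inflation is in absolute size. Coverage there is 0% by construction, because a term is kept exactly when its 90% interval excludes zero.

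**Number of tests.** For five independent tests at 0.10, the chance of at least one false positive is 1 − 0.9^5 = 0.41. Simulated backward elimination over five main effects and five interactions, with no true interaction, kept at least one in 46% of trials at N=40 and 45% at N=50.

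**Hypothesis 2b.** This was simulated at N=40 and a single time point, with four candidate covariates having effects of 0–8 items per SD and correlations of 0–0.4 with SSRI use (all assumed).
- Covariates unrelated to SSRI use: the SSRI estimate was unbiased, and 95% intervals covered 0.949–0.951.
- Covariates related to both SSRI use and outcome: selection by significance left a bias of about 2–4 items, with coverage 0.926–0.946.
- All four covariates fixed in advance: coverage 0.949–0.952.

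The bias was positive here because the assumed correlations and effects shared a sign. With opposite signs it would reverse.

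**The case against.** The strongest reply is that these are labelled exploratory, that the plan concedes low power for the SSRI question, and that the primary analysis is untouched: its covariates (aphasia type, AQ, age) are fixed in SAP 8.2. All of that is correct and limits the importance of the point. The label does not make a selected estimate unbiased, however.

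It can also be said that the SAP defines a final model without saying other estimates will be withheld, and that its code would display arm-by-subgroup results without pruning. That is fair. The documents do not establish that dropped terms would go unreported; the inflation arises if the sentence governs. The conflict between sentence and code is itself a reason to amend.

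Three stronger readings are tempting and are not supported:
- A reader might infer that the SSRI effect in Hypothesis 2b is itself exaggerated and its interval invalid. The SSRI term is not selected by p-value, three adjustment terms are already fixed, and the simulated loss of coverage was small.
- A reader might take the 41% as a consequence of the retention rule. It comes from the level and the number of tests, and reporting every term leaves it unchanged.
- A reader might infer that the subgroup interactions are declared inputs to the next trial. The documents say this of SSRI use. The protocol's Phase III remark in the same paragraph as the rule concerns fMRI versus structural electrode placement, which is not subject to it.

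**Conclusion.** The point holds for the retention rule. Under even subgroups and SD 22.2, surviving interactions average about 25 to 30 items in absolute size when the truth is 0 or 10. Ordinary 90% intervals reach about nominal coverage only when the true interaction is as large as the planned treatment effect; even then the mean kept estimate is 32–34 against a truth of 23. Unequal subgroups would raise the standard error and worsen the inflation; a residual SD reduced by covariate adjustment would lessen it.

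For Hypothesis 2b the point is narrower. Choosing the additional covariates by significance leaves the model unspecified in advance and can omit real confounders. The consequence is residual confounding in either direction, about 2–4 items in the scenarios tried. This should be corrected before unblinding, but it does not threaten the primary conclusion.

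**What to change.** 1. Delete the retention sentence from SAP section 11. SAP section 2 gives the final SAP precedence over the protocol, so the protocol's copy need not block this.
2. Close the list of characteristics. Report each interaction from the pre-specified arm-by-subgroup model with its estimate and 90% interval, whatever its p-value, in line with the existing code. The present output statement gives cell means and pairwise differences, so add a statement for the interaction contrast itself.
3. State the number of interaction tests beside the table, with the roughly 41% chance of at least one false positive among five independent tests. Full reporting removes the selection bias but not this.
4. For Hypothesis 2b, keep arm, baseline naming accuracy and time, and replace the significance criterion with named covariates: AQ, aphasia type, age and days from stroke onset.

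The cost is SAP wording, one extra line of code and a few more rows in a table. SAP section 2 already provides for an update before database lock and unblinding.
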